Add-on to NCT03280355

Statistical Analysis Plan for a long-term follow-up study in RCT “The Effects of Singing Training for Patients with Chronic Obstructive Pulmonary Disease (COPD)” (NCT03280355).

Document date: 06/19/2023

Title of follow-up study:

Long-term upkeep of activity, effects, and impact following pulmonary rehabilitation for COPD with either Singing for Lung Health or physical exercise training.

Study Information

In our recent multicentre RCT - *Sing-a-Lung 1.0* - comparing Singing for Lung Health (SLH) with usual-care physical exercise training (PExT) within 10 week's community-based pulmonary rehabilitation (PR) for COPD (NCT03280355), we demonstrated that SLH conferred relevant short-term improvements regarding both physiological and psychological parameters and was non-inferior to PExT.¹⁻³ Post-hoc analyses demonstrated that effect was correlated with adherence in both groups,⁴ and, moreover, suggested that SLH was associated with improved inspiratory muscle control and dyspnoea control, and that a larger proportion in SLH achieved the minimal important difference (MID) in quality of life (QoL) (measured by change in St George's Respiratory Questionnaire; SGRQ; MID = ≤ 4 units) than in physical capacity (measured by change in 6-Minute Walk Test Distance; 6MWD; MID = ≥ 30 m) (49% vs. 29%).⁵

Little is, however, known about the long-term effects of SLH including upkeep of activity, effects, and life-style changes, which is a well-known significant challenge within PR with PExT.⁶⁻⁸

Aims and hypotheses

With the present project - *Sing-a-Lung 1.1* - we will conduct a long-term follow-up study within the study cohort of *Sing-a-Lung 1.0* (n=270; SLH n=145/PExT=125) to investigate long-term upkeep of activity. Secondarily, we will investigate sustainability of effect and impact on quality of life, anxiety, depression, and dyspnoea. Furthermore, we aim to obtain deeper insight into how the study participants have integrated the tools derived from participating in either SLH or PExT.

Specifically, we aim to investigate:

Primary study outcome and hypotheses:

1. Whether level of adherence demonstrated in *Sing-a-Lung 1.0* is correlated with upkeep of activity. We hypothesise that high adherence in *Sing-a-Lung 1.0* predicts high long-term upkeep of activity after *Sing-a-Lung 1.0* and vice versa for low adherence. Moreover, we hypothesise that SLH is non-inferior to PExT in upkeeping long-term activity.

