The present study is a long-term follow-up study of upkeep of activity and sustaining of effects across RCT study groups in *Sing-a-Lung 1.0* (SLH and PExT) using validated and specially developed questionnaires to facilitate descriptive and comparative analyses and to conduct mixed-methods inspired research equivalent to our previously published, survey-based research. The validated questionnaires cover QoL, dyspnoea, and symptoms of anxiety and depression, and are all specifically validated and used for COPD. The specially developed questionnaires were developed by PostDoc, Ph.d., [name] in close collaboration with Ph.d., Consultant in Pulmonology, [name], and discussed and settled with the additional research group members: Professor, Ph.d., Consultant in Pulmonology, [name]; Professor, D.MS.c, Consultant in Pulmonology, [name]; and Associate Professor, D.MS.c, Consultant in Pulmonology, [name].

Randomisation

Participants were randomised during the *Sing-a-Lung 1.0* RCT (Trial registration number: NCT03280355). The intervention phase of *Sing-a-Lung 1.0* took place between August 2017 and May 2019.

Sampling Plan

Existing Data

Already collected data from *Sing-a-Lung 1.0* include:

- Basic baseline characteristics: *e.g.* age, BMI, socio-demographics, smoking history, health care utilisation, exacerbations, medicine, comorbidities, and expectations towards benefits of singing.
- Baseline and short-term follow-up data related to *Sing-a-Lung 1.0* outcomes: Physical Capacity (Six-Minutes Walking Test; 6MWT), Quality of Life (St Georges' Respiratory Questionnaire; SGRQ), anxiety and depression (Hospital Anxiety and Depression Scale; HADS), dyspnoea (BORG-CR10 and Modified Medical Research Scale, mMRC), lung function (Forced Expiratory Volume in one Second; FEV1% predicted and Forced Vital Capacity; FVC% predicted), respiratory muscle strength and control (inspiratory pressure, breath counting scale, breath holding test), adherence, drop-out-rate, medicine consumption, number of COPD-related hospitalisations and exacerbations, and satisfaction with study intervention.

Sample size

RCT cohort of *Sing-a-Lung 1.0* (n=270). Participants who accept to participate will be included in the study. The following participants will be excluded from analyses: 1) Do not accept to participate, 2) Not reachable via telephone (after three attempts at different dates), 3) Deceased since *Sing-a-Lung 1.0*.

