Data collection procedures

Participants from *Sing-a-Lung 1.0* have already provided written consent for a long-term follow-up contact. All participants will therefore be contacted directly by telephone by the research assistant Department of Medicine, Hospital Lillebaelt, Vejle, during February to May 2023 and asked for their consent to participate in the follow-up study. The research assistant will collect data by telephone and data will be entered directly into web-based, software survey tool and secure database, SurveyXact by Ramboll (Rambøll Management Consulting, Aarhus, Denmark)¹⁰ which will be used for survey distribution, data collection, and data storage. PostDoc, Ph.d., [name], is in charge of the overall data collection.

Data analysis procedures

In June 2023, data will be transferred from the database at SurveyXact by Ramboll to Microsoft Excel file and imported into statistical software STATA 17 (StataCorp LLC, Texas, USA). Data will be anonymised, cleaned and prepared (see section: Analysis plans/Modifications of specific variables of interest to be included in the logistic regression models) before merging with the original dataset and related 1:1 to observations from *Sing-a-Lung 1.0*. Merging and subsequent analysis process will start July 2023.

Variables

Measured variables

For the long-term follow-up study, data collection includes current smoking status, and patient-reported health care utilisation, exacerbations, and usage of COPD-related medicine since *Sing-a-Lung 1.0*. Besides, the data collection includes patient-reported knowledge on availability of local structured or unstructured offer of singing, for example a lung choir, and on availability of local structured or unstructured offer of physical training after the intervention.

Furthermore, we will collect data related to the following outcomes and variables of interest:

Study outcomes	Measure
Primary study outcome	
1. Long-term upkeep of activity	
Participation in local, structured or unstructured singing activity, for example a lung choir.Participation in local, structured or unstructured upkeep course in physical training.Participation in any other activity (physical, musical, or creative).Overall self-evaluated level of physical and social activity compared to before intervention.
Secondary study outcomes	

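### Upkeep by adherence and by arm is compared only in survivors who were reached and agreed; losses are not crossed with arm, and selective response is neither tested nor fully corrected for

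*SAP*

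**What the plan says.** Under Sampling Plan, Sample size, the SAP states "The following participants will be excluded from analyses: 1) Do not accept to participate, 2) Not reachable via telephone", continuing "after three attempts at different dates), 3) Deceased since" the original trial. The source cohort is given under Aims and hypotheses as "n=270; SLH n=145/PExT=125". The primary hypotheses there are that adherence during the RCT predicts later upkeep, and: "Moreover, we hypothesise that SLH is non-inferior to PExT in upkeeping long-term activity".

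Timing comes from three places. The course ran "within 10 week's community-based pulmonary rehabilitation (PR) for COPD" (Study Information). The intervention phase "took place between August 2017 and May 2019" (Randomisation). Participants are telephoned "during February to May 2023" and "asked for their consent to participate in the follow-up study" (Data collection procedures).

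The SAP does look at selection descriptively. Under Analysis Plan, Overall, characteristics and performance are to be explored in three groups: the included, those who declined or were not reached (one pooled group), and the deceased. The deceased are also split by low, medium and high adherence. Randomised arm is a separate item in that list.

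Adjusted and unadjusted logistic models are planned. Data analysis procedures refers to a section on variables for those models, and that section lists, among others, adherence, arm, age, FEV1% predicted and baseline 6MWD. It does not say which variable enters which model. The SAP names no weighting, imputation, bounding or other sensitivity analysis for non-response.

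**The concern.** Randomisation protects the arm comparison only while the people analysed are those randomised, or a subset selected in a way that is not tied jointly to arm and outcome. Here the analysed set is fixed years later by surviving, being reached and agreeing. The assistant who telephones is blinded, which limits unequal contact effort. Participants know which course they took, however, so blinding cannot prevent unequal refusal. The adherence comparison was never randomised, and willingness to attend sessions may share causes with willingness to answer a follow-up call.

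If non-respondents are less active and the PExT arm responds better, the respondent analysis flatters SLH; if the SLH arm responds better, it understates SLH. The plan as written would not show the make-up of losses by arm, and would not test how far the conclusions depend on who answered.

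**Working it through.** **Inputs from the SAP.** SLH 145 and PExT 125 (145 + 125 = 270, as stated); a 10-week course; intervention August 2017 to May 2019; contact February to May 2023. The SAP gives no upkeep, response or death rate, so every rate below is an assumption.

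**Interval since the course.**
- Longest: 1 August 2017 plus 10 weeks is 10 October 2017; to 31 May 2023 is 5.64 years.
- Shortest: 31 May 2019 to 1 February 2023 is 3.67 years.

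**Hidden difference, same gap in both arms.** Let respondents' upkeep be 50% in both arms, r the response among survivors, and g the amount by which non-respondents' upkeep is lower. Survivor upkeep is 0.50r + (0.50 − g)(1 − r) = 0.50 − (1 − r)g. An observed arm difference of 0 then hides (r_S − r_P)g:

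| Response difference | g = 10 points | g = 20 points | g = 30 points |
|---|---|---|---|
| 10 points (60% vs 50%) | 1 | 2 | 3 |
| 20 points (70% vs 50%) | 2 | 4 | 6 |

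**Hidden difference, equal response but unequal gaps.** Take 60% response in both arms.
- SLH, g = 30 points: 0.50 − 0.40 × 0.30 = 38%.
- PExT, g = 10 points: 0.50 − 0.40 × 0.10 = 46%.

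Eight points are hidden although losses are perfectly balanced.

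**Second route to the same conclusion.** Let true upkeep be 40% in both arms. Suppose keepers and non-keepers respond at 70% and 50% in SLH, and at 60% and 60% in PExT.
- SLH observed: 0.28/(0.28 + 0.30) = 48.3%.
- PExT observed: 40.0%.

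That is a spurious 8.3 points with overall response of 58% vs 60%. With the harsher 80% and 40% in SLH, the observed figure is 0.32/(0.32 + 0.24) = 57.1%, a spurious 17.1 points. The answer is driven by the assumption.

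**Sampling error for comparison.** Half-width = 1.96 × √(0.25/n_S + 0.25/n_P), with n_S = 145(1 − d)r_S, n_P = 125(1 − d)r_P and d the proportion dead.

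| Response SLH / PExT | d = 0 | d = 35% |
|---|---|---|
| 50% / 60% | 16.1 points | 20.0 points |
| 50% / 70% | 15.6 | 19.3 |
| 60% / 50% | 16.2 | 20.2 |
| 70% / 50% | 15.8 | 19.5 |
| 60% / 60% | 15.4 | 19.2 |

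For the last row, n is 87 and 75 with no deaths: 1.96 × √(0.25/87 + 0.25/75) = 0.154; dividing by √0.65 gives 0.192.

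**Adherence.** The hidden-difference formula applies equally to two adherence classes, but the SAP gives no class sizes, so no half-width can be set beside it.

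**Cost of weighting.** Variance inflation is mean(w²)/mean(w)² among respondents.
- Half of survivors responding at 40% and half at 80%: 1.125, so the standard error rises by a factor of √1.125 = 1.061.
- 30% and 70%: 1.190, a factor of 1.091.

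**Size of the response model.** With 15% or 35% dead, 229.5 or 175.5 are alive. At 50% to 70% response the smaller of the responder and non-responder groups is 52.7 to 114.8 people. Nine terms would leave 5.9 to 12.8 people per term, which is too few at the low end. Five terms leave 52.7/5 = 10.5 to 114.8/5 = 23.0.

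**The case against.** Several counter-arguments carry weight.

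- **Partly unavoidable.** The outcome is a telephone questionnaire after fresh consent, and upkeep is undefined for the dead. No analysis plan can recover these data. This stands; the point asks for disclosure and a sensitivity check.
- **Selection is already described.** A reader might infer that the plan ignores those lost. It does not: it compares the included, the lost and the deceased, and splits deaths by adherence. What remains is the missing cross with arm, the pooling of refusal with non-contact, and their missing split by adherence.
- **Adjustment already does part of the work.** If response depends only on variables in the fitted model, regression among respondents gives valid conditional associations, and several likely predictors are on the SAP's list. This stands, subject to the list being assigned to models. It does not cover other measured variables, such as baseline SGRQ, or response driven by upkeep.
- **Total loss by arm can be worked out.** The denominators 145 and 125 are given, so any arm-level result reveals total loss. True, but not its division into death, refusal and non-contact.
- **Loss counts may mislead.** A reader might infer that balanced losses would clear the comparison. The equal-response example shows that they would not, and imbalance alone does not give the size of any bias.
- **Small beside sampling error.** In the 1-to-6-point and 8-point cases this is so. The interval, however, displays sampling error and not selection.

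The STROBE commitment concerns reporting and names no analysis, so it does not close the gap.

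**Conclusion.** The point holds as a cheap improvement. The adherence and arm comparisons of upkeep rest on survivors who were reached and agreed. The plan describes those losses without crossing them with arm, and contains nothing that tests or corrects for response depending on upkeep itself or on measured variables outside its candidate list.

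The stated sizes (1 to 6 points with a common gap, 8 points with equal response and unequal gaps, against a half-width of about 15 to 20) rest wholly on assumed rates: 50% upkeep in respondents, gaps of 10 to 30 points, response of 50% to 70%, deaths of 0 to 35%. No size is offered for adherence.

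A reader might go further and infer that the comparison is biased towards SLH, or that a non-inferiority conclusion would be invalid. The SAP supports neither: it gives no response rates, and the bias could run either way or be absent.

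**What to change.** 1. Tabulate death, refusal and non-contact separately, by arm and by the SAP's adherence classes, including the zero class, which the planned split of deaths leaves out.
2. Beside the respondent analysis, add one sensitivity analysis among participants not known to have died. Use inverse-probability-of-response weights from a short prespecified set of predictors already held, for example arm, sessions attended, age, FEV1% predicted and baseline SGRQ. Add a simple range in which non-respondents' upkeep is set lower by amounts allowed to differ between arms, for instance 0 to 30 points in each.
3. Word the adherence and arm conclusions as applying to survivors who answered, whatever step 2 shows. Agreement with a weighted analysis cannot exclude response that depends on upkeep.

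Cost: a little analysis time and no new data. The SAP is dated 19 June 2023 and places merging and analysis from July 2023, so on its own timetable the change fits before analysis. Downsides: weighted standard errors about 6% to 9% larger on the assumed response rates, correction only for measured predictors, and some unreachable participants may in fact have died.

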2. Whether short-term follow-up scoring values in QoL, anxiety, depression, and dyspnoea sustains at long-term follow-up. We hypothesise that SLH is non-inferior to PExT regarding sustaining of scoring and effect demonstrated in *Sing-a-Lung 1.0*.

Secondary study outcomes, and hypotheses:

- A. Whether short-term achievement of effect in QoL – defined as achievement of MID or not in SGRQ – is associated with upkeep of activity and scoring values. We hypothesise that those who achieved MID are more likely to maintain/upkeep or seek out an activity and keep up scoring values.
- B. Whether self-reported long-term level of overall physical and social activity is associated with RCT randomisation, hypothesising that SLH is non-inferior to PExT.

Whether RCT randomisation is associated with self-reported satisfaction with intervention, experienced relevance, and experienced integration of the tools obtained, hypothesising that SLH is non-inferior to PExT.

C. Whether availability of a local, structured upkeep course in physical training or a lung choir is correlated to long-term upkeep of activity, hypothesising that available local, structured offer improves likelihood of upkeep of activity. Furthermore, we hypothesise that SLH is non-inferior to PExT regarding likelihood of upkeep of activity.

Design Plan

Study type

The present study is an observational study, based on a follow-up study in the RCT cohort of *Sing-a-Lung 1.0* (n=270) (Trial registration number: NCT03280355; project title: “The Effects of Singing Training for Patients with Chronic Obstructive Pulmonary Disease (COPD)”).

Blinding

The research assistant responsible for data collection is blinded to RCT randomisation. After the analysis process, blinded results (presented as A: Level of adherence 0 compared to Level of adherence 1; and B: Treatment 0 compared to Treatment 1) will be presented to the research group, who will interpret the blinded results. Prior to unblinding of the trial results, the research group will prepare two alternative conclusions for Level of adherence and two alternative conclusions for randomisation.⁹

Study design

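### Hypothesis C is about availability of a local structured offer, but the variable collected is the participant's awareness of any offer, and attending an offer is part of upkeep

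*SAP*

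**What the plan says.** In the SAP, item C of the secondary hypotheses first asks "Whether availability of a local, structured upkeep course in physical training or a lung choir is correlated to long-term upkeep of activity". It then gives a direction: "hypothesising that available local, structured offer improves likelihood of upkeep of activity". The exposure named there is availability, and the offer is a structured one.

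Under Measured variables, the data on availability are "patient-reported knowledge on availability of local structured or unstructured offer of singing, for example a lung choir", and the same kind of knowledge "on availability of local structured or unstructured offer of physical training after the intervention". Both were to be asked by telephone between February and May 2023. No source independent of the participant is named.

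In the list of modified variables under Statistical models, item 7 is a yes/no variable for an available offer of singing or physical training. It no longer says that the source is the participant's knowledge. It does not say where a participant who does not know belongs, or whether unstructured offers count.

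The outcome table gives four measures of upkeep. Two are "Participation in local, structured or unstructured singing activity, for example a lung choir" and "Participation in local, structured or unstructured upkeep course in physical training". The others are any other activity and a self-evaluated activity level.

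**The concern.** There are two mismatches between C and its variable: awareness stands in for availability, and structured or unstructured stands in for structured.

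The first mismatch matters because of the outcome. Someone who attends a local choir or course knows that it exists. Someone who does not attend may be unaware of one nearby. Error in the exposure therefore depends on the outcome. Covariate adjustment in the planned logistic models does not repair this.

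At stake is the conclusion drawn from C. A positive result could be read as evidence that providing offers improves upkeep, when part or all of it may only show that active people know of the offers they use.

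**Working it through.** The SAP gives no effect size, power or awareness figure for C, so there is no planned figure to reproduce. The check asks what association would be seen if offers did not change overall upkeep.

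**Inputs, all assumed except alpha**
- a = share of participants with an offer: 0.6, 0.7, 0.8
- s = among those with an offer, share of upkeep that runs through it: 0.25, 0.5, 0.75
- k = awareness among those with an offer who do not attend it: 0.6, 0.7, 0.8, then 0.9, 0.95 and 1
- attenders are all aware, and nobody without an offer reports one
- upkeep means any participation, 46% overall
- 150 analysed. The cohort of 270 is a ceiling, because deaths, refusals and unreachable participants are excluded.
- alpha 0.05 from the SAP, taken as two-sided; chi-square test; counted only when significant in the direction of C, so 2.5% is expected

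**No effect, 'does not know' coded as no offer.** Let m = s + (1 − s)k, the awareness among people who keep up activity and have an offer. Then

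OR = m(1 − ak) / [k(1 − am)],

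which does not depend on the upkeep rate. At the midpoint (a = 0.7, s = 0.5, k = 0.7), m = 0.5 + 0.5 × 0.7 = 0.85, and OR = 0.85 × 0.51 / (0.7 × 0.405) = 0.4335 / 0.2835 = 1.53.

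**No effect, 'does not know' coded as missing.** OR = m / k = 0.85 / 0.7 = 1.21. This assumes that people without an offer say there is none equally often whether or not they keep up activity. If those who keep up are more than 1.21 times as likely to say so, the bias reverses.

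| Setting (no true effect, n = 150) | OR | Significant in favour of C |
|---|---|---|
| Coded no offer, midpoint | 1.53 | 25% |
| Coded no offer, 27 combinations with k 0.6 to 0.8 | 1.13 to 2.79 | 6% to 85% |
| Coded missing, midpoint | 1.21 | 7.6% |
| Coded missing, same 27 combinations | 1.06 to 1.50 | 4% to 21% |
| Coded no offer, a = 0.7, s = 0.5, k = 0.9 | 1.17 | 6.4% |
| Coded no offer, a = 0.7, s = 0.5, k = 0.95 | 1.08 | 4.2% |
| Coded no offer, k = 1 | 1.00 | 2.5% |

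The percentages are simulated, with at least 200,000 data sets per setting.

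**Real effect.** Take upkeep of 60% with an offer and 40% without, so the true OR is (0.6 × 0.6) / (0.4 × 0.4) = 2.25. With no-offer coding, a = k = 0.7 and s = 0.25, the four cells are:
- reports an offer, upkeep: 0.42 × 0.775 = 0.3255
- reports an offer, no upkeep: 0.28 × 0.7 = 0.196
- does not report one, upkeep: 0.42 × 0.75 × 0.3 + 0.3 × 0.4 = 0.2145
- does not report one, no upkeep: 0.28 × 0.3 + 0.3 × 0.6 = 0.264

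The observed OR is 0.3255 × 0.264 / (0.196 × 0.2145) = 2.04, below the truth. With s = 0.5 it is 2.63, above it. Over a and k from 0.6 to 0.8, the ranges are 1.91 to 2.19 and 2.43 to 2.90.

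**The case against.** The SAP is open about much of this. It calls the data patient-reported knowledge, states that "The present study is an observational study", and first asks only about a correlation. Known availability is a reasonable exposure for a telephone survey. All of that stands, and it keeps the importance low. It does not settle the point, because item 7 drops the qualifier and C still predicts an improvement.

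The numbers are also open to challenge, with good reason:
- The 25% rests on a coding that the SAP does not state. The questionnaires are not at hand, so it cannot be told whether not knowing was a possible answer, or whether structured and unstructured offers were asked about separately.
- The documents do not exclude awareness of 90% or more among non-attenders, and the bias is then small.
- No effect requires offers to attract attenders and yet leave overall upkeep unchanged. At the midpoint, upkeep outside the offer would have to be 23% where an offer exists, against 46% where none does. At s = 0.75 it would have to be 11.5%, which is an extreme case.
- The overlap is partial. Unstructured participation need not be in an offer that was asked about, and two of the four upkeep measures do not directly overlap with the offer.

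A reader might infer that the plan will inflate the association, or that false support for C is likely. The documents support neither. The upward direction is shown only under no effect and the stated coding assumptions; under a real effect the bias can run either way. The high error rates come from assumed corners of the range.

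**Conclusion.** The point holds as a mismatch between the claim and its measure. Item C speaks of availability of a structured offer and of improvement. The data can speak only to awareness of some offer, and upkeep partly consists of attending such offers. The association can therefore differ from 1 without any effect of offers on overall upkeep.

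The size is not determined by the SAP. It runs from negligible to large, depending on how not knowing is coded, how many non-attenders are aware, and how much upkeep runs through the offers. Importance is low: one secondary hypothesis is affected, and neither the adherence question nor the comparison of randomised groups in the primary aims depends on this variable.

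**What to change.** Before merging and analysis start in July 2023, change the wording of the SAP:

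1. Rename item 7 as awareness of a local offer, with singing and physical training as separate variables.
2. Code participants who do not know either as their own category or as not aware; do not code them as having no offer available.
3. State whether unstructured offers count, and make C match.
4. Restate C as whether awareness of a local offer is associated with upkeep, and remove the claim that an offer improves it.

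Telephone collection was planned to end in May 2023, so none of this touches the questionnaire. The cost is a few lines of text. The downside is that C then supports no statement about the effect of providing offers. The new label also does not remove the overlap: attenders remain aware by definition, so the result should be reported as descriptive.

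Retrospective course listings are not part of this fix. They would need outside records and a centre variable that the SAP's list of existing data does not name.

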Modifications of specific variables for analyses: 1) Adherence during RCT (ranging from 0 to 20 sessions attended; classified into three categories: zero: 0%; low: 1-49%; medium: 50-74%; high: 75-100%), 2) Intervention randomisation, 3) Sustaining of effects: QoL, anxiety, depression, dyspnoea or not (all related to minimal important difference, MID (4 units for SGRQ and 1 for HADS and mMRC), 4) Achievement of MID in RCT (SGRQ and 6MWD) or not, 5) Age categorised into quartiles, 5) FEV1% predicted categorised according to GOLD (1-4),^{6,8} 6) Baseline 6MWD categorised into quartiles, 7) Available offer of singing/physical training or not.

STROBE Statement checklist for cohort studies will be used for reporting. Statistical analyses will be performed using statistical software STATA 17 (StataCorp LLC, Texas, USA). Statistical significance will be reported as $p < 0.05$.

Ethics

Written consent for long-term follow-up contact was provided in *Sing-a-Lung 1.0* and as the long-term-follow-up study, moreover, will be solely questionnaire-based, ethical approval from The Committee on Health Research Ethics was not required. The study was approved by The Danish Act on Processing of Personal Data regarding re-accesses to the raw data of *Sing-a-Lung 1.0* in order to retrieve patients' contact information and to conduct the new questionnaire-based study of the long-term-follow-up study (REG-135-2022).

Feasibility

The long-term follow-up study will be managed and facilitated by PostDoc, Ph.d., [name]. The study will be conducted at Pulmonary Research Unit Zealand (PLUZ), Zealand University Hospital Roskilde and Naestved Hospital. Furthermore, Medical and Respiratory Department, Hospital Lillebaelt, Vejle, will participate with academic qualification and advice and will donate salary for the research assistant responsible for data collection.

Funding

Funding has been obtained from the following funding bodies: The Danish Health Foundation (DKK 200.000), The Danish Lung Foundation (DKK 100.000), Region Zealand Chiesi Pharma AB (DKK 85.000). The research assistant responsible for data collection was employed and paid by Hospital Lillebaelt.

Dissemination

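### Hypothesis 2 by arm: coding long-term SGRQ, HADS and mMRC as sustained or not at the MID discards information that a baseline-adjusted analysis of scores already held would keep

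*SAP*

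**What the plan says.** - **Coding.** Under Modifications of specific variables for analyses, item 3 makes a yes/no variable: "Sustaining of effects: QoL, anxiety, depression, dyspnoea or not (all related to minimal important difference, MID (4 units for SGRQ"; the other two scales, HADS and mMRC, are cut at 1. The item names no reference visit, direction or inequality. Data analysis procedures describes the listed variables as "Modifications of specific variables of interest to be included in the logistic regression models".
- **Hypothesis 2.** The aim is "Whether short-term follow-up scoring values in QoL, anxiety, depression, and dyspnoea sustains at long-term follow-up", which leans to the short-term visit as reference. The next sentence reads "We hypothesise that SLH is non-inferior to PExT regarding sustaining of scoring and effect demonstrated in" the RCT. Sustaining an effect can also mean change from baseline.
- **Hypothesis A.** The predictor is short-term benefit, "defined as achievement of MID or not in SGRQ" (item 4 of the list). The expectation is: "We hypothesise that those who achieved MID are more likely to maintain/upkeep or seek out an activity and keep up scoring values".
- **Models.** Statistical models, Overall, plans MID cut-offs for the validated questionnaires, tests for continuous data of several kinds, and adjusted and unadjusted logistic regression. It names no covariate for the continuous tests.
- **Data held.** Existing Data lists baseline and short-term SGRQ, HADS and mMRC from the RCT.

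**The concern.** Hypothesis 2 asks whether singing is non-inferior to exercise training in what remains at long-term follow-up. A non-inferiority question is decided by the width of an interval, so precision matters. Cutting each score at its MID treats a patient just inside the threshold as equal to one far inside it. Leaving out the baseline score also gives up a strong predictor that costs nothing to use.

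The second concern is narrower. The SAP does not name item 3 as the outcome for the scoring-values half of hypothesis A. However, the only outcome-table entry for these scores is the sustaining of effect, MID cut-offs are prescribed, and the listed variables go into the logistic models. If SGRQ item 3, or an SGRQ change score, is used there, outcome and predictor contain the same visit's SGRQ measurement. Its transient error then enters both sides.

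**Working it through.** The SAP gives no figure to reproduce here, and no SDs or expected number of respondents.

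**Assumptions (SGRQ).** True score SD 16. True 10-week change: mean -2 to -3, SD 5. Error SD 4-6 per visit. Later change: mean +2, SD 6-16. The upper end allows for the long interval: the intervention phase "took place between August 2017 and May 2019", and participants are called "during February to May 2023 and asked for their consent to participate in the follow-up study", so 3.75 to 5.75 years. All parts are taken as independent. These inputs give 39.5-46.0% MID achievers; Study Information reports 49% in the singing arm.

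Notation: BL = T + e1, ST = T + d + e2, LT = T + d + c + e3, with d the 10-week change and c the later change.

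**1. Information for the arm comparison.** Central case: error SD 5, later-change SD 8, 10-week mean -3.

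- ANCOVA on baseline: Var(LT | BL) = 256 + 25 + 64 + 25 - 256²/281 = 370 - 233.2 = 136.8.
- Yes/no coding, for a small shift, relative to ANCOVA: [φ(z)² / (p(1-p))] × 136.8 / Var(change).
- Baseline reference, LT - BL ≤ -4: variance 25 + 64 + 50 = 139, SD 11.79, mean -1, z = -3/11.79 = -0.254, φ = 0.386, p = 0.400. Result: 0.622 × 136.8/139 = 0.61.
- Short-term reference, LT - ST < 4: variance 64 + 50 = 114, SD 10.68, mean 2, z = 2/10.68 = 0.187, φ = 0.392, p = 0.574. Result: 0.629 × 136.8/114 = 0.75.

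Simulation with a 2-unit arm effect over the whole grid gave 0.61-0.64 (baseline reference) and 0.67-0.84 (short-term reference). The second range holds only if the arm effect arises after the short-term visit. An effect gained in the RCT and retained is invisible to that coding, which answers a different question.

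The unspecified continuous tests may or may not repair this. In the same case, an unadjusted comparison of LT keeps 136.8/370 = 0.37, and a comparison of change from baseline keeps 136.8/139 = 0.98.

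**2. Coupling in hypothesis A (conditional).** The predictor is ST - BL ≤ -4.

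- Short-term reference, gain fully retained by everyone: Cov(d + e2 - e1, c + e3 - e2) = -σe².
- Baseline reference, nothing retained (LT = T + c + e3): Cov(d + e2 - e1, c + e3 - e1) = +σe².

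In the central case both correlations have size 25/√(75 × 114) = 0.27, with opposite signs. Over 24 scenarios the error-free odds ratio is 0.99-1.01 or 1.00-1.01. With error:

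| Rule for sustained | Odds ratio, achievers vs non-achievers |
|---|---|
| LT - ST < 4 | 0.39-0.73 |
| LT - BL ≤ -4 | 1.4-2.7 |
| \|LT - ST\| < 4 | 0.82-0.97 |

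Central case: 0.480 vs 0.652 sustained gives (0.480/0.520)/(0.652/0.348) = 0.49 for the first rule; 0.368 vs 0.219 gives (0.368/0.632)/(0.219/0.781) = 2.08 for the second.

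A second set of assumptions (10-week change SD 8-14, drift 0-8, 49% achievers) varied the transient share of the 10-week change. The first rule then gave 0.23-0.25 if all of it is transient, about 0.5 at half, and 1.00 if none is. The second gave about 4 and upwards; where changes are permanent, part of that is true carry-over.

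**The case against.** **The SAP already allows continuous analyses.** This stands in part. The 60-85% applies where the result rests on the yes/no variable. A test of change from baseline would lose little, and an unadjusted test of the long-term score would lose more than the yes/no coding. The SAP does not say which test is meant, so the good choice is permitted but not fixed.

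**Aim 2 asks about loss since the short-term visit, which ANCOVA on baseline does not estimate.** True. This is why the MID result should stay, and why ANCOVA is offered only for how much effect remains by arm.

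**Hypothesis A is not tied to item 3.** Correct. Its words also allow the long-term score itself, which has no shared visit when left unadjusted for SGRQ. The coupling point is therefore conditional.

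**A reader might infer that measurement error alone makes the answer to A flip with the reading chosen.** The documents do not support that. The two null odds ratios come from different situations, all retained and nothing retained. With zero error the readings still disagree: 0.14-0.46 for the short-term rule when nothing is retained, and 2.2-7.1 for the baseline rule when all is retained. They ask different questions. Nor is a symmetric rule, which the SAP's wording also admits, much affected.

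**A reader might also infer that the arm comparison is biased.** It is not. Arms were randomised, and nothing in this coding favours either.

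**Conclusion.** The point holds as a loss of precision that is cheap to repair. For hypothesis 2, the yes/no SGRQ coding keeps roughly 60-85% of the information of a baseline-adjusted analysis. With 150 respondents (assumed) that is like analysing 90 to 128 of them (150 × 0.60 and 150 × 0.85). The figure rests on assumed SDs and was worked out for SGRQ only. For HADS and mMRC the same direction is expected, but no size is given.

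The coupling in hypothesis A is real if an SGRQ change, MID-coded with a one-sided rule or as a raw change, is tested between SGRQ achievers and non-achievers. Its direction follows from the shared error. Its size depends on assumptions, and the short-term effect vanishes if the 10-week change has no transient part. The scope is one scale in half of one secondary hypothesis. Upkeep of activity, HADS and mMRC do not share a measurement with the predictor and are not affected by this coupling.

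**What to change.** 1. For hypothesis 2, add an ANCOVA of long-term SGRQ, HADS anxiety, HADS depression and mMRC on randomised arm, each adjusted for the RCT baseline of the same score, as the analysis of how much effect remains by arm. Keep the MID yes/no result as a description of loss since the short-term visit.
2. In item 3, state for each scale the reference visit, the direction and the inequality that define sustained, before the long-term data are merged with the RCT data.
3. For hypothesis A, do not read a test of SGRQ sustained, or of SGRQ change, by SGRQ achiever status as evidence for or against the hypothesis. Report it descriptively with a regression-to-the-mean caveat. The long-term SGRQ score by achiever status, unadjusted for SGRQ, may be shown alongside as a comparison of level.

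Cost: SAP wording and a few model runs, since all scores are held or being collected. Limits: ANCOVA gives the effect left, not the loss since the short-term visit. The level comparison does not measure maintenance and has low power (17-43% with 150 respondents under the assumptions above). It can also be confounded: with a correlation of -0.1 to -0.2 between true baseline and true 10-week change, achievers look 1.3-3.4 units worse when nothing is retained.
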